**Exploratory:**

Variation of the oncology treatment dosage (dose intensity).

## 3. STUDY DESIGN

Multicentric, randomized, open-label trial of comparison of planned, continuative nurse monitoring intervention together with an information sheet with advice about prevention and treatment of treatment-related toxicities – chemotherapy-, targeted therapy- or immunotherapy-related ones versus the exclusive use of the same information sheet.

### 3.1 Study population

Every patient with a solid tumour treated with adjuvant chemotherapy or targeted therapy or immunotherapy for metastatic disease will be included.

In the second and third group patients receiving either targeted therapies or immunotherapies will be eligible.

The following inclusion and exclusion criteria are valid for all groups:

#### ***Inclusion criteria***

- Patients aged 18 or over.
- Histological diagnosis of solid tumour treated with the following drugs (defined per group):

- Adjuvant chemotherapy:
  - anthracyclines and cyclophosphamide ± taxanes (breast cancer)
  - oxaliplatin and fluoropyrimidines (colon cancer)
  - combination of platinum or its derivatives (lung cancer)
- Oral targeted therapy:
  - sunitinib, pazopanib (kidney cancer)
  - gefitinib, erlotinib, afatinib, crizotinib (lung cancer)
  - vemurafenib ± cobimetinib, dabrafenib ± trametinib (melanoma)
  - everolimus ± exemestane (breast cancer)
  - aromatase inhibitors + CDK4/6 inhibitors (breast cancer)
  - fulvestrant + CDK4/6 inhibitors (breast cancer)
  - vandetanib, lenvatinib (thyroid cancer)
  - vismodegib (cutaneous basal cell carcinoma)
  - imatinib (GIST)
- Immunotherapy:
  - anti-CTLA4 drugs,
  - anti-PD-1/PDL-1 drugs,
  - their combination.
- Written consent signature;
- Availability, and accessibility, for phone contact;
- Life expectancy  $\geq$  6 months.

***Exclusion criteria:***

- Presence of symptomatic brain metastases;
- Presence of neurological and psychiatric diseases or other conditions that may prevent patients from being compliant to protocol procedures;
- Prior exposure to systemic oncological treatment. This criterium is justified by the fact that having received a previous oncological treatment usually causes an alteration of the toxicity profile and in these cases, the attention to toxicity is higher and patients often receive other preventive treatments.
- Participation in other clinical trials.
- 

**3.2 Patients'classification and randomisation**

Eligible patients are split up into three subgroups according to the oncological treatment

- Patients on adjuvant chemotherapy
- Patients treated with oral targeted therapy for the first time
- Patients treated with immunotherapy for the first time

Within each subgroup patients are randomised to receive:

- ✗ a periodical nurse monitoring phone call, that is planned and agreed with the patient, together with an information sheet with advice about prevention and treatment of toxicities (Experimental group)
- ✗ an information sheet with advice about prevention and treatment of toxicities (Standard group).

1:1 randomisation will be performed via computer using the randomly permuted blocks system.

All participants are to give their written informed consent.

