## **4. OPERATIVE ASPECTS**

The realisation of the study was preceded by a programme of training meetings about supportive therapies in patients receiving oncological treatments. These meetings were organized in the entire national territory. At least one oncologist in each of the 63 centres that have joined the trial participated in these meetings.

During these meetings, an information dashboard has been developed and shared. This dashboard, that is useful for both the physician and the patients, contains the best supportive therapy for every administered oncological treatment (according to the expected toxicities).

This dashboard was developed with the help of several health professionals (physicians and nurses) and the support of a board of specialists (dermatologists, gastroenterologists, cardiologists, endocrinologists). It is formed by a synthetic sheet that is customized according to the oncological treatment, based on the expected treatments.

This intervention, based on either national and international guidelines (AIOM, NCCN, MASCC, ASCO) is the standard for the prevention and treatment of therapy-related toxicities.

The study provides the randomisation between the use of the information sheet and the addition of a periodical nurse monitoring intervention that is planned and agreed with the physician. The nurse team that is in charge of the monitoring interventions is centralized (Nurse Operation Center) and is adequately trained about the potential toxicities that may come out during the study. The team has a function of coaching and training and supports the patient's empowerment (see Appendix 1 – Service guide).

The nurse monitoring intervention consists of a weekly phone call throughout the entire period of treatment and it follows a protocol of predefined and individualized questions in order to evaluate the toxicities according to the treatment group. During the empowerment phone call, the patient is encouraged to adopt the correct protocols for prevention and cure according to the specific oncological treatment.

The possible actions that may arise during the phone call (codified in the nurse algorithm) may be:

- a) advice on the use of drugs and therapeutic/preventive actions according to the information dashboard;
- b) facilitation of the contact of the patient with the referral specialists and/or general practitioner in case of toxicities that do not need an urgent intervention (within 12 hours);

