## **5.3 Data analysis**

Qualitative variables are synthesized in absolute frequencies and percentages; quantitative ones through mean and standard deviation, maximum and minimum, median and interquartile range. The evaluation of the statistical significance of the differences between two main groups (nurse monitoring vs standard monitoring) will be analyzed through the Student's t-test for dependent groups in case of quantitative parameters. The chi-square test will be used to evaluate the statistical significance of the differences in qualitative parameters. The comparisons among groups will be performed at the end of the study. The statistical significance of the variations in time of quantitative variables will be performed through the two-way analysis of variance (ANOVA). A secondary analysis will be performed, aiming at evaluating the statistical significance of the differences in all the other parameters between the two groups.

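### Groups B and C pool several cancer regimens with 50 patients per arm, and the stated between-arm tests do not adjust for regimen: a modest, cheap loss of precision, not a bias

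*Protocol*

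**What the plan says.** Section 3.2 splits patients into adjuvant chemotherapy (A), oral targeted therapy (B) and immunotherapy (C). It then states "Within each subgroup patients are randomised to receive" nurse calls plus information sheet, or the sheet alone. On the method it says "1:1 randomisation will be performed via computer using the randomly permuted blocks system". Treatment class is therefore a stratum, and no finer factor is named.

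The inclusion criteria in section 3.1 show what each class contains. Group C takes "anti-CTLA4 drugs", "anti-PD-1/PDL-1 drugs" or the two combined. Group B lists nine drug lines across seven tumour types (kidney, lung, melanoma, breast, thyroid, basal cell carcinoma, GIST). Group A has three adjuvant regimens.

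Section 4 describes a dashboard that "contains the best supportive therapy for every administered oncological treatment (according to the expected toxicities", with a sheet tailored to each treatment. The protocol thus treats expected toxicity as depending on the drug, but gives no rate by regimen.

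Section 5.3 says the difference between nurse and standard monitoring "will be analyzed through the Student's t-test for dependent groups in case of quantitative parameters", with a chi-square test for qualitative ones. Two-way ANOVA is mentioned only for change over time. No stated between-arm test has a regimen term.

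Section 5.1 sets 50 per arm in each of B and C (25% to 5%, power 0.72) and 207 per arm in A (15% to 5%, power 0.9). Accrual in A is complete.

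**The concern.** The regimen is known before randomisation, because it determines eligibility and which sheet the patient receives. If regimens within a class differ in the number of days with grade 3 or higher toxicity, that variation sits in the error term of an unadjusted test. With 50 per arm, the arms can also differ by chance in their share of the more toxic regimens. An unadjusted comparison does not correct for this, and an adjustment chosen after an imbalance is seen is less credible than one fixed beforehand. Groups B and C were reduced to a stated power of 0.72, so precision is scarce there.

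**Working it through.** **1. The plan's own figures.** For 25% versus 5%, two-sided alpha 0.05 and power 0.72 (z = 1.96 and 0.583):

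- Uncorrected n = [1.96·√(2·0.15·0.85) + 0.583·√(0.25·0.75 + 0.05·0.95)]² / 0.20² ≈ 40.5, that is 41.
- With continuity correction, n = (40.5/4)·[1 + √(1 + 4/(40.5·0.20))]² ≈ 50.

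The same method gives 207 for Group A, and 2·207 + 4·50 = 614. All three figures reproduce and are not in question.

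**2. Size of chance imbalance.** Assume a share q of a group is on a higher-toxicity regimen and approximate the blocks by an exact equal split of the group (hypergeometric). The documents do not give q.

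| Arm size | q | SD of difference in share | P(≥10 points) | P(≥20 points) |
|---|---|---|---|---|
| 50 (B or C) | 20% | 8 points | 21% | 2% |
| 50 (B or C) | 50% | 10 points | 32% | 7% |
| 207 (A) | 20% | 4 points | 1% | about 0 |
| 207 (A) | 50% | 5 points | 5% | about 0 |

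**3. Effect on the arm difference in B or C.** Shift = imbalance × gap between regimen rates. The rates are assumed: two equal classes averaging the protocol's 25%, from 15%/35% (moderate) to 5%/45% (extreme).

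- A 10-point imbalance shifts the difference by 0.10·0.20 = 2 points to 0.10·0.40 = 4 points.
- A 20-point imbalance shifts it by 4 to 8 points.
- For comparison, the planned effect is 20 points and the standard error under no effect is √(2·0.25·0.75/50) = 8.7 points.
- Given a 20-point imbalance, the unadjusted test (no continuity correction) has type I error of about 7% to 12%. If the imbalance disfavours the nurse arm, power falls from 86–87% to 77% (moderate) or 66% (extreme).
- With regimen exactly balanced, the same test rejects under no effect only 4.4% (moderate) or 2.8% (extreme) of the time.

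**4. Averaged over randomisation, yes/no outcome.** 20,000 simulated trials per scenario, 50 per arm, planned 80% relative reduction. The adjusted test is Cochran-Mantel-Haenszel (CMH) by regimen.

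| | 15%/35% | 5%/45% |
|---|---|---|
| Type I error, current blocks, unadjusted | 5.0% | 4.9% |
| Type I error, current blocks, CMH | 4.9% | 4.8% |
| Power, current blocks, unadjusted | 85.0% | 85.3% |
| Power, current blocks, CMH | 84.3% | 87.9% |
| Power, regimen-stratified blocks, CMH | 85.0% | 88.4% |

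These powers exceed 0.72 because no continuity correction is used. Adjustment is worth about 0 to 3 points, and slightly less than zero in the moderate case with the current blocks.

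**5. Days outcome.** The primary objective in section 2 is a number of days, so the yes/no calculation is not the closest model. Variance between two equal classes is 0.25·gap², that is 0.25·0.20² = 0.01 to 0.25·0.40² = 0.04.

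- For a yes/no outcome, total variance is 0.25·0.75 = 0.1875. Regimen explains 5% to 21% of it, and removing that narrows the standard error by 1 − √(1 − 0.053) = 3% to 1 − √(1 − 0.213) = 11%.
- A per-patient proportion of days varies less than a yes/no event, so the same gap explains more. Simulation of such an outcome at 50 per arm, with the same rates, keeps type I error near 5% and narrows the standard error by about 5% to 20% under no effect. That corresponds to regimen explaining 1 − 0.95² = 10% to 1 − 0.80² = 36% of the variance, or a between-patient SD of about √(0.01/0.0975) = 0.32 to √(0.04/0.36) = 0.33.
- The power gain is about 0.5 to 2 points at the planned 25% to 5%, where power is already near its ceiling, and about 3 to 13 points if the rate is only halved.

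**The case against.** The strongest reply is that nothing is wrong. Treatment class is already a stratum, and the only toxicity rates in the protocol (15% for A, 25% for B and C) differ between classes that randomisation separates. Chance imbalance is part of what the test's 5% allows for, and on a yes/no outcome adjustment gains almost nothing. Covariate adjustment may also appear in a statistical analysis plan that is not shown.

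Much of this stands. A reader might infer that the nurse effect estimate is biased or that false positives are inflated. The documents do not support that: averaged over randomisation the estimate is unbiased, and the raised conditional error after an unlucky draw is offset by a lower one when the arms are balanced. A reader might also infer that regimens within a class are known to differ greatly in severe toxicity. Section 4 supports only that expected toxicities depend on the treatment, and the gaps used above are assumptions. Nor does the point weigh much on Group A, which has 207 per arm.

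Two parts do not stand. The near-zero gain is specific to a yes/no outcome, whereas the objective is days. And the point does not rest on silence: section 5.3 names its between-arm tests, and they carry no regimen term.

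**Conclusion.** The point holds as an inexpensive improvement for Groups B and C. The stated comparison leaves regimen variation in the error term and leaves a chance imbalance uncorrected: a between-arm difference of 10 points or more in the share of a higher-toxicity regimen has probability 21% to 32%. The benefit of adjustment ranges from about nothing (yes/no outcome, moderate gap) to about 13 power points (days outcome, extreme gap, effect half the baseline rate). At the planned effect on days it is about 0.5 to 2 points. All of these sizes rest on an assumed regimen mix, assumed regimen rates and, for days, an assumed between-patient spread. If regimens within a class hardly differ in severe-toxicity days, the gain is close to zero. The sample sizes in section 5.1 are unaffected.

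**What to change.** In section 5.3, state that the nurse versus standard comparison of grade 3 or higher days within B and within C is adjusted for, or stratified by, a few broad regimen classes. Fix the classes before any outcome is compared by arm. Examples are single agent versus combination in C, and two or three merged drug classes in B. The same approach is optional for A, using the breast, colon and lung regimens.

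The cost is analysis wording, since the regimen is already known for every patient from eligibility. The drawback is that Group B has nine drug lines in 100 patients, so sparse classes must be merged, and the protocol gives no basis for how. The sponsor should record its reasons. Changing the randomisation strata during accrual is not required; in the yes/no simulation it adds only 0.5 to 0.7 power points beyond adjustment (88.4 − 87.9 and 85.0 − 84.3).

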### **3.3 Study duration**

The study will last 24 months. Patients' accrual will have a duration of 18 months, from the beginning of the trial. The study period will be 4 months for the immunotherapy and targeted therapy groups and 6 months for the adjuvant chemotherapy group.

The study can be interrupted earlier in case of oncological treatment discontinuation because of disease progression, unacceptable toxicity, or withdrawal of consent by the patient, or patient's death. In case of temporary suspension of the oncological treatment, patients will continue to be monitored according to the group they are assigned. The study ends with the end of the monitoring period, that is with the last phone call to the last enrolled patient.

## **4. OPERATIVE ASPECTS**

The realisation of the study was preceded by a programme of training meetings about supportive therapies in patients receiving oncological treatments. These meetings were organized in the entire national territory. At least one oncologist in each of the 63 centres that have joined the trial participated in these meetings.

During these meetings, an information dashboard has been developed and shared. This dashboard, that is useful for both the physician and the patients, contains the best supportive therapy for every administered oncological treatment (according to the expected toxicities).

This dashboard was developed with the help of several health professionals (physicians and nurses) and the support of a board of specialists (dermatologists, gastroenterologists, cardiologists, endocrinologists). It is formed by a synthetic sheet that is customized according to the oncological treatment, based on the expected treatments.

This intervention, based on either national and international guidelines (AIOM, NCCN, MASCC, ASCO) is the standard for the prevention and treatment of therapy-related toxicities.

The study provides the randomisation between the use of the information sheet and the addition of a periodical nurse monitoring intervention that is planned and agreed with the physician. The nurse team that is in charge of the monitoring interventions is centralized (Nurse Operation Center) and is adequately trained about the potential toxicities that may come out during the study. The team has a function of coaching and training and supports the patient's empowerment (see Appendix 1 – Service guide).

The nurse monitoring intervention consists of a weekly phone call throughout the entire period of treatment and it follows a protocol of predefined and individualized questions in order to evaluate the toxicities according to the treatment group. During the empowerment phone call, the patient is encouraged to adopt the correct protocols for prevention and cure according to the specific oncological treatment.

The possible actions that may arise during the phone call (codified in the nurse algorithm) may be:

- a) advice on the use of drugs and therapeutic/preventive actions according to the information dashboard;
- b) facilitation of the contact of the patient with the referral specialists and/or general practitioner in case of toxicities that do not need an urgent intervention (within 12 hours);
- c) in case of toxicities that need an urgent intervention (less than 12 hours): facilitation of the contact with the referral physician or, if the contact is not possible, suggestion to access to the hospital through the centre-specific modalities (access

to the emergency room, access to the supportive care service, and so on);

d) in case of not deferrable urgencies: direct access to the emergency room through the emergency services (118).

At the end of every phone call, the Nurse Operative Center gives a synthetic report of the detection and sends an appropriate email to the reference physicians (identified at the moment of randomisation).

During the evaluation period, according to the PRO-CTCAE (validated in Italian) (53) (Attachment 1, 2, 3), in both groups, a questionnaire for the monitoring of toxicities will be administered to each patient.

This questionnaire, which takes into consideration the previous week, monitors the frequency (F), severity (S), and intensity (I) of each symptom. A question about the number of days spent with toxicity will be performed. The administration of the questionnaire will be made through a pre-registered phone call (without an operator), which is based on an electronic score coding. This phone call does not overlap with the monitoring phone call in the specific randomisation group.

For the patients' privacy, every date coming from the project will be dealt with according to the current laws.

In each group, at the baseline visit, then every month, the EORTC QLQ-C30 questionnaire (Attachment 4) will be administered.

In both groups, there will be a monitoring activity of the number of unplanned hospital accesses (emergency room or specialist visits). An evaluation of the number of hospital admissions and days of hospital stay (due to toxicities) will be performed.

Finally, the dose intensity of the oncological drugs throughout the period of treatment will be monitored (it will be considered as the ratio between the administered dose and the planned dose). This aspect is fundamental not only for the management of the oncological therapy but also for the adherence to the recommendations of supportive care.

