## 2. OBJECTIVES

**Primary:** To evaluate the number of days patients spend with a grade 3 or higher toxicity (among those considered). The specific toxicities that are the object of evaluation are chosen among those that are clinically relevant and are more likely responsible for a reduction of treatment adherence and, then, a reduction of the benefit from such treatment.

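### In groups B and C, symptoms present before the first dose can enter the patient-reported count of toxicity days, with no stated pre-treatment PRO-CTCAE rating; the likely cost is power, not bias

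*Protocol*

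**What the plan says.** The primary objective (Protocol, section 2) reads "To evaluate the number of days patients spend with a grade 3 or higher toxicity (among those considered".

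Section 4 describes how toxicity is recorded in both arms. Its timing is given as "During the evaluation period, according to the PRO-CTCAE (validated in Italian". On content it says: "This questionnaire, which takes into consideration the previous week, monitors the frequency (F), severity (S), and intensity (I) of each symptom". A further item asks for the number of days with toxicity. The call is pre-recorded, with no operator on the line. For baseline, the same section mentions only the quality-of-life instrument: "at the baseline visit, then every month, the EORTC QLQ-C30 questionnaire".

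On population, section 3.1 takes in patients "treated with adjuvant chemotherapy or targeted therapy or immunotherapy for metastatic disease will be included". I read the metastatic setting as applying to groups B (oral targeted therapy) and C (immunotherapy). The only exclusion that names tumour symptoms is "Presence of symptomatic brain metastases". Prior systemic cancer treatment is also an exclusion.

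Section 6.2.2 has adverse reactions graded by CTCAE 4.03, and section 6.2.3 asks the investigator to rate causality for every adverse event. Neither section connects those ratings to the day count. Section 5.3 plans t-tests and chi-square tests between arms and names no baseline covariate.

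**The concern.** The endpoint is meant to capture harm from treatment. The instrument rates symptoms, and nobody on the call can ask what caused them. Because previously treated patients are excluded, a symptom present before the first dose cannot be toxicity of the monitored drug or of an earlier systemic one. Yet the protocol states neither a pre-treatment rating that would identify such a symptom nor a rule that would remove it from the count.

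The nurse calls and the information sheet are directed at treatment toxicity. If disease symptoms enter the count and the calls leave them alone, they add similar days to both arms. The difference between arms can shrink and the spread between patients grows. With 50 patients per arm, a few highly symptomatic patients can also fall unevenly between arms, with no pre-treatment PRO-CTCAE value to adjust for. Groups B and C are planned at a power of only 0.72, so there is little to give away.

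This goes beyond what can be left to an analysis plan: a rating not taken before treatment cannot be recovered later.

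**Working it through.** **1. Is there another filter or baseline?** Setting sections 2, 4, 6.2.2 and 6.2.3 side by side:
- Days with toxicity are collected in one described place, the automated questionnaire in section 4.
- That section gives a baseline to QLQ-C30 only.
- The causality rating applies to adverse events in the eCRF. No sentence uses it to include or exclude questionnaire days.

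So pre-existing symptoms can be counted. Whether they are depends on how patients answer.

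**2. Reproduce the plan's own figures.** Inputs from section 5.1: groups B and C, 25% against 5%, alpha 0.05, 50 per arm, power 0.72; group A, 15% against 5%, 207 per arm, power 0.9. The two-sided, continuity-corrected two-proportion formula is

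power = Φ{ [d − 1/n − 1.96·√(2p̄(1−p̄)/n)] / √([p1(1−p1) + p2(1−p2)]/n) }

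with d = p1 − p2 and p̄ the mean of p1 and p2.

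For B and C: (0.20 − 0.02 − 0.1400)/0.0686 = 0.58, and Φ(0.58) = 0.72. The same formula gives 0.90 for group A. Both stated designs are reproduced.

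**3. Disease symptoms as part of the planned 25%.** The planned effect is a relative reduction of (25 − 5)/25 = 80%. Let a share s of the 25% be disease symptoms that the calls do not change. Then the nurse arm has

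p2 = 0.25·s + 0.25·(1 − s)·0.2

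| s (assumed) | Control | Nurse arm | Difference | Bracket in the formula | Power, 50 per arm |
|---|---|---|---|---|---|
| 0 | 25% | 5% | 20 points | 0.0400/0.0686 | 0.72 |
| 10% | 25% | 7% | 18 points | 0.0163/0.0711 | 0.59 |
| 20% | 25% | 9% | 16 points | −0.0073/0.0734 | 0.46 |
| 40% | 25% | 13% | 12 points | −0.0538/0.0775 | 0.24 |

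**4. Disease symptoms on top of the planned rates.** Let a share b of all days carry severe disease symptoms in both arms, so that p′ = b + (1 − b)p. With b = 5%, 10% and 20%, the rates are 28.75% against 9.75%, 32.5% against 14.5%, and 40% against 24%. Power is 0.58, 0.47 and 0.32.

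**5. The other end of the range.** If the calls cut disease-symptom days by the same 80%, then p2 = 0.25·s·0.2 + 0.25·(1 − s)·0.2 = 0.05 for any s, and power stays at 0.72. The loss therefore depends on both the disease share and how far the calls act on it. The documents give neither.

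**The case against.** Five points can fairly be made on the other side.

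- **The day item asks about toxicity, not symptoms.** A reader might infer that a patient entering with severe cancer symptoms is bound to be scored with severe toxicity from the first call. The text does not establish that, because some patients will leave such days out. What remains is that attribution rests on the patient alone. The item wording is in attachments not shown, as is the list of toxicities that count.
- **Section 2 does not name PRO-CTCAE as the source.** If the days came from investigator-graded events with a causality rating, the problem would largely go away. But the protocol describes no count of days from that source.
- **Randomisation balances symptoms at entry.** A reader might infer a bias between arms. There is none on average, and chance imbalance is already covered by alpha. The loss of precision stands, as does the value of a baseline covariate for recovering some of it.
- **The Background does not document the problem.** A reader might take its mention of pain and dyspnoea as evidence of disease symptoms. That sentence concerns unplanned visits caused by chemotherapy toxicity. The Background does distinguish symptoms of cancer from toxicity of therapy in general terms, but gives no frequency of severe symptoms at entry. The life-expectancy criterion of at least 6 months and the brain-metastasis exclusion will remove some of the sickest patients.
- **Nurse calls may relieve disease symptoms too**, since they route patients to physicians and supportive care. Dilution would then be smaller, as step 5 of the working shows.

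None of these supplies the missing pre-treatment rating or a rule for pre-existing symptoms.

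**Conclusion.** The point holds in a limited form. In groups B and C, severe symptoms that predate treatment can enter the only described count of toxicity days if patients do not separate them from toxicity. The consequence is extra variance, possible dilution and exposure to chance imbalance at 50 per arm. It is not systematic bias.

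The size cannot be taken from the documents. A fall in power from 0.72 to between 0.59 and 0.24 rests on two assumptions: that 10% to 40% of the planned 25% is disease symptoms, and that nurse calls do not change them. It also takes the plan's two-proportion formula, and its 25%, at face value; section 5.1 itself describes the 25% as an estimate made for lack of data. The change is worth making because it is cheap and the planned power leaves little margin.

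**What to change.** **Section 5.3.** Replace the unadjusted primary comparison with one adjusted for baseline QLQ-C30 symptom scores, within each treatment group, and name the scores in advance. These data are already collected, so this costs nothing in the field. Adjustment recovers precision and handles chance imbalance in symptoms at entry. It does not take disease days out of the count.

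**Section 4.** Add one automated PRO-CTCAE call before the first dose, in both arms, for patients still to be enrolled in groups B and C. Use it in a supportive analysis only: either adjust for the baseline rating or count days rated worse than baseline. Keep the primary day count the same for all patients, so that the endpoint is not redefined during the trial. Counting only worsening has its own limits: progression also worsens symptoms, and a patient at the top rating at entry cannot worsen on that item.

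**Cost.** One extra call without an operator per new patient and a short amendment to two sections. The baseline rating will be missing for patients already enrolled, so the supportive analysis covers only part of groups B and C.
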